### **3. Data Collection**

The EMR will be reviewed to collect preoperative, intraoperative, and POD 0 data points. We will use the following method to identify the occurrence of a procedure-related adverse event: The EMR will be reviewed for patient phone calls for a procedure-related complication, unscheduled office visits, emergency department visits, hospital readmissions or reoperations within 30 days, and adverse events occurring up to 6 weeks post-operatively. The adverse events of interest will include the following:

- Wound infection
- Hematoma
- Transfusion
- Pelvic abscess
- Osteomyelitis
- Venous thromboembolism (deep vein thrombosis or pulmonary embolism)
- Delayed bowel or urinary tract injury
- Bowel obstruction or ileus
- Cardiac or pulmonary complication
- Neurologic injury

We will also employ an approach that will allow us to capture events that may have been handled outside of the CCHS or in institutions that do not utilize *Epic*. To capture these data points if they exist, we will contact participants by telephone on POD 1 (within 24 hours of surgical completion time) to determine if they received any care from a facility outside of the CCHS and then again at the post-operative follow up visit, which generally occurs at 6 weeks. We will then use these data with the Clavien Dindo Scale to determine the severity of the adverse event, with a grade 3 or higher considered to be a serious adverse event, and we will compare this proportion to the reference proportion of 26.3%. A proportion of patients with grade 3 or higher less than 45.1% will be considered non-inferior to the reference.

As part of the effort to characterize the patient population, we will extract data regarding total procedure-related costs using the EMR. We will assess satisfaction using the quality of recovery questionnaire, visual analog scores for postoperative pain, and a patient satisfaction survey described by Fountain et al at the postoperative visit, which uses a Press Ganey scale for responses (See Appendix A). Please see data collection sheet for a comprehensive list of planned data points.

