*Sample size:* We estimate that approximately 80 minimally invasive sacrocolpopexy surgeries will be performed per year. Of these, we anticipate that ~3/4 will meet eligibility criteria and of these patients, ~3/4 will consent to participate. Based upon data by Unger et al, a Clavien Dindo grade 3 adverse event (defined as requiring surgical, endoscopic, or radiologic imaging/intervention) was identified in 26.3% of patients after a minimally invasive sacrocolpopexy. A meta-analysis of laparoscopic versus open sacrocolpopexy combined results of 9 randomized control-trials and found a post-operative complication rate of 5.4% after minimally invasive sacrocolpopexy (robotic and laparoscopic). We suspect that 26.3% may be an overestimation of adverse events as the Unger et al study included any imaging required in the postoperative period even if the result was normal. However, we also suspect that a 5.4% adverse event incidence may be low. As such, we feel that an adverse event incidence of 12% may be more representative of that expected after this surgical procedure.

We used a one-sided exact test for non-inferiority of binomial proportion to determine the degree of difference between the proportion of 26.3% and an incidence proportion greater than the reference which could be detected and deemed inferior (significantly greater) to the reference with a power of 80%. With a sample size of 45 patients, the proportion of patients with a Clavien Dindo grade of 3 will need to be 45.1% or greater. We will account for a 3% drop out rate (based on 2016 post-operative visit "no-show" rates for the Urogynecology division) by recruiting an additional 2 patients, making the sample size planned for this study a total of 47 patients.

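### The primary non-inferiority rule applies 45.1%, a true rate taken from the power calculation, as a cut-off on the observed proportion, so 18 to 20 events in 45 pass although significantly above 26.3%

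*Combined protocol and SAP*

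**What the plan says.** Section 1 (Study Design) makes serious adverse events the primary outcome. Section 3 (Data Collection) defines these as Clavien Dindo grade 3 or higher, says "we will compare this proportion to the reference proportion of 26.3" per cent, and gives the decision rule: "A proportion of patients with grade 3 or higher less than 45.1% will be considered non-inferior to the reference".

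The source of 45.1% is the sample-size paragraph of section 4 (Statistical Plan). It describes a one-sided exact binomial calculation for a rate above 26.3% that could be "deemed inferior (significantly greater) to the reference with a power of 80" per cent, and concludes that with 45 patients "the proportion of patients with a Clavien Dindo grade of 3 will need to be 45.1% or greater".

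The statistical-analysis paragraph of section 4 gives 0.05 as the significance level. It plans 95% confidence intervals for categorical variables and a comparison with 60 historical controls discharged on day 1. It compares no interval with a margin, and it states no margin for the comparison with controls.

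**The concern.** A power calculation involves two different numbers. One is the critical value, which is the observed result at which the test rejects. The other is the detectable alternative, which is the true rate at which the test rejects with the chosen power. The alternative always lies further from the reference than the critical value. If 45.1% is the alternative, then using it as the threshold for the observed proportion lets through results that the planned test would reject.

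A non-inferiority claim also needs the data to exclude an unacceptable rate, normally by a confidence limit lying below a margin. A point estimate below a number does not do that. Nor is 45.1% justified clinically: it follows from n = 45 and 80% power. It lies 45.1 − 26.3 = 18.8 percentage points above the reference.

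At stake is the only stated decision rule for the primary safety outcome, and with it the hypothesis in Background & Significance that same-day discharge is as safe as discharge on day 1.

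**Working it through.** **Inputs.** n = 45, reference p0 = 0.263, one-sided exact binomial test and 80% power (section 4, Sample size); level 0.05 (section 4, Statistical analysis; not tied explicitly to the exact test); acceptance rule of an observed proportion below 45.1% (section 3). X is the number of patients with a grade 3 or higher event, X ~ Bin(45, p).

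**Step 1. Reproduce 45.1%.** The critical value is the smallest r with P(X ≥ r | 0.263) ≤ 0.05.

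- P(X ≥ 17) = 0.0608, which is too large.
- P(X ≥ 18) = 0.0312, so r = 18, an observed 18/45 = 40.0%.

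Solving P(X ≥ 18 | p) = 0.80 gives p = 0.4515, and power at p = 0.451 is 0.798. This reproduces the plan's figure. At one-sided 0.025 the critical value is 19 and the detectable rate is 47.4%, which does not match. So 45.1% is a true rate under the alternative, for a one-sided 5% test whose observed cut-off is 40.0%.

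**Step 2. What the section 3 rule accepts.** 20/45 = 44.4% is below 45.1%, and 21/45 = 46.7% is above it. The rule passes 20 or fewer.

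| Events of 45 | Observed | One-sided p against 26.3% | Section 3 rule |
|---|---|---|---|
| 17 | 37.8% | 0.061 | non-inferior |
| 18 | 40.0% | 0.031 | non-inferior |
| 19 | 42.2% | 0.015 | non-inferior |
| 20 | 44.4% | 0.006 | non-inferior |
| 21 | 46.7% | 0.003 | not non-inferior |

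At 20/45 the one-sided 95% exact (Clopper-Pearson) upper limit is 57.7%.

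**Step 3. How often the rule passes.**

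| True rate | P(X ≤ 20), rule passes | P(18 ≤ X ≤ 20), passes though significantly higher |
|---|---|---|
| 26.3% | 99.7% | 2.9% |
| 40% | 77.8% | 33.4% |
| 45.1% | 52.6% | 32.5% |
| 50% | 27.6% | 20.8% |

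**Step 4. Sensitivity to the number evaluable.** The plan recruits 47 to allow for 3% drop-out.

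| Evaluable n | Section 3 passes at | Exact 5% test rejects at | P(pass) at a true 45.1% |
|---|---|---|---|
| 43 | ≤ 19 | ≥ 17 | 51.5% |
| 44 | ≤ 19 | ≥ 17 | 46.1% |
| 45 | ≤ 20 | ≥ 18 | 52.6% |
| 46 | ≤ 20 | ≥ 18 | 47.3% |
| 47 | ≤ 21 | ≥ 18 | 53.7% |

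At least three counts conflict at every n.

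**Step 5. 45.1% treated as a proper margin.** Test H0: p ≥ 0.451 at one-sided 5% with n = 45. P(X ≤ 14 | 0.451) = 0.040 and P(X ≤ 15 | 0.451) = 0.074, so the pass count is 14 or fewer. Equivalently, the one-sided 95% upper limit is 44.3% at 14 events and 46.6% at 15. Power is P(X ≤ 14 | 0.263) = 0.818. At one-sided 2.5% the pass count is 13 or fewer, with power 0.720.

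Two valid cut-offs therefore follow from the plan's own numbers: at most 17 (no significant increase over 26.3%) and at most 14 (45.1% excluded). Neither is 20.

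**The case against.** **The two sections agree as worded.** Both speak of 45.1% as the dividing line, and neither states a critical count or a level for the exact test. That is so: the count of 18 is inferred. But the inference is firm, because among the exact tests tried only the one-sided 5% level reproduces 45.1%. At one-sided 2.5%, 18 events would no longer be significant, but 19 and 20 still would. The agreement in wording only means that both sections treat a true-rate alternative as an observed threshold.

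**The conflict is unlikely to arise in practice.** At a true 26.3%, 18 to 20 events occur in 2.9% of trials, and at 12%, the rate the plan tentatively expects, in fewer than 0.01%. This stands as a statement about expected rates. It does not defend the rule, because a safety criterion is judged by what it does when the treatment is worse, and this one passes a true 40% in 78% of trials.

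**Other analyses give protection.** Confidence intervals will be reported, so the uncertainty at 20/45 (two-sided exact 95% interval 29.6% to 60.0%) would be visible. The comparison with 60 controls adds evidence. Both help a careful reader, but neither is tied to a margin, so neither changes the declared conclusion.

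**The choice of reference is a separate matter.** The plan says "We suspect that 26.3% may be an overestimation of adverse events" and that "an adverse event incidence of 12% may be more representative of that expected after this surgical procedure". It does not say whether imaging alone will count as grade 3 in the new cohort. This is a real ambiguity, but nothing in the calculations above depends on it.

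**Conclusion.** The concern holds. The 45.1% is correctly calculated but applied to the wrong quantity. With 45 evaluable patients, 18 to 20 events would be declared non-inferior although the test behind the sample size finds them significantly above 26.3%. The rate the study was sized to detect as inferior passes about half the time: 52.6% at n = 45, and 46% to 54% for 43 to 47 evaluable. This rests on exact binomial probabilities, the plan's reference of 26.3%, and the one-sided 5% level inferred from the plan's own figure. At one-sided 2.5% the conflict narrows to 19 and 20 events. No assumption about the 12% rate is needed. This must be corrected before the primary analysis, because a pass under the present rule cannot support a claim of equal safety.

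**What to change.** 1. Replace the decision sentence in section 3 with: *Non-inferiority will be concluded if the one-sided 95% exact (Clopper-Pearson) upper confidence limit for the proportion of patients with a grade 3 or higher event is below L.* Fix L and justify it clinically before analysis. State the rule by the limit and not by a count, since the count changes with the number evaluable.
2. Restate the sample-size paragraph of section 4 with L, the level, the pass count and the power at n = 45, so that it matches section 3.
3. Specify that the interval reported for the primary outcome is the one used for the decision. At 14/45 the one-sided 95% limit is 44.3%, but the upper end of a two-sided 95% interval is 46.7%. If the two-sided interval is to govern, 45.1% would be met at 13 or fewer, with 72.0% power at a true 26.3%.
4. Label the comparison with the 60 controls as supportive.

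**Cost.** These are text changes in two sections. Keeping L = 45.1%, purely as an illustration, needs no added patients: 45 patients give 81.8% power at a true 26.3% and a 4.0% chance of passing a true 45.1%. The pass threshold becomes stricter (14 in place of 20), and power is sensitive to losses. With 44 evaluable the pass count is 13 and power falls to 75.0%. Power stays at or above 80% only from 47 evaluable patients, which is the whole planned recruitment. A smaller L would reduce power further at a true 26.3%, and the restated calculation should show this.

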### **4. Statistical Plan**

*Statistical analysis:* Categorical variables will be presented as n/N (%) with 95% confidence intervals. Continuous variables will be presented as mean +/-SD or median [range]. A Pearson's chi-square test or Fisher exact test will be used for frequencies and proportions of categorical values and t test or the non-parametric Wilcoxon rank sum test for mean values of continuously measured variables. P values  $\leq 0.05$  will be considered statistically significant and we will use SAS (version 9.4, The SAS Institute, Cary NC) as our statistical package to perform these analyses. The primary investigator will perform the statistical analysis with assistance from the WHI statistician.

We will use data from a historical control group discharged on POD 1 after minimally invasive sacrocolpopexy to examine Aim 1 and Aim 2. This is a cohort of 60 women matching our eligibility criteria from a prospective randomized trial of two different types of lightweight polypropylene mesh (IRB #14-354). This study completed recruitment 2017. It consists of a group of women who underwent minimally invasive sacrocolpopexy using the same surgical approaches, at the same institutions (main campus, Fairview and Hillcrest), and performed by the same surgeons as our study. The primary difference is that participants in that study and the cohort proposed here is that all participants were discharged home on POD 1. We will utilize this cohort to compare the incidence and severity of procedure-related adverse events and costs between SDD and POD 1. Comparisons on outcome measures will be done using either an ANOVA analysis or a student's t test for parametric continuous outcomes, a Kruskal-Wallis or Mann Whitney U test for non-parametric outcomes and a Chi-square test for all categorical outcomes. Logistic regression will be performed to control for confounding variables.

*Sample size:* We estimate that approximately 80 minimally invasive sacrocolpopexy surgeries will be performed per year. Of these, we anticipate that ~3/4 will meet eligibility criteria and of these patients, ~3/4 will consent to participate. Based upon data by Unger et al, a Clavien Dindo grade 3 adverse event (defined as requiring surgical, endoscopic, or radiologic imaging/intervention) was identified in 26.3% of patients after a minimally invasive sacrocolpopexy. A meta-analysis of laparoscopic versus open sacrocolpopexy combined results of 9 randomized control-trials and found a post-operative complication rate of 5.4% after minimally invasive sacrocolpopexy (robotic and laparoscopic). We suspect that 26.3% may be an overestimation of adverse events as the Unger et al study included any imaging required in the postoperative period even if the result was normal. However, we also suspect that a 5.4% adverse event incidence may be low. As such, we feel that an adverse event incidence of 12% may be more representative of that expected after this surgical procedure.

We used a one-sided exact test for non-inferiority of binomial proportion to determine the degree of difference between the proportion of 26.3% and an incidence proportion greater than the reference which could be detected and deemed inferior (significantly greater) to the reference with a power of 80%. With a sample size of 45 patients, the proportion of patients with a Clavien Dindo grade of 3 will need to be 45.1% or greater. We will account for a 3% drop out rate (based on 2016 post-operative visit "no-show" rates for the Urogynecology division) by recruiting an additional 2 patients, making the sample size planned for this study a total of 47 patients.

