### **Background & Significance**

Enhanced recovery after surgery (**ERAS**) pathways play a critical role in the delivery of high-quality surgical care. These protocols incorporate multiple perioperative patient interventions including preemptive analgesia, measures to reduce postoperative nausea and emesis, fluid balance aimed at euvolemia, and both early ambulation and oral intake. ERAS pathways are significant because they have been shown to shorten recovery, decrease hospital stay, reduce complications/nosocomial infections, and conserve resources. Same-day discharge (**SDD**) is a central aspect of enhanced recovery pathways.

**SDD and ERAS protocols are part of a new initiative within the Women's Health Institute**, and their application for gynecologic surgery is of increasing interest across the country. To date, the focus of studies has largely been on laparoscopic and robotic hysterectomy in the benign and gynecologic oncology literature. Studies have consistently demonstrated both feasibility and safety of SDD after laparoscopic and robotic hysterectomy, with no significant increase in complications or readmissions as compared to discharge on postoperative day (**POD**) 1. In fact, a recent systematic review by Korsholm et al of 15 observational studies with nearly 12,000 patients revealed SDD is feasible, at a rate of nearly 80%, when patients are properly selected and careful surgical planning is performed. Studies have also demonstrated high patient satisfaction and less cost with SDD after minimally invasive hysterectomy. SDD has been applied in other minimally invasive gynecologic procedures, such as minimally invasive myomectomy, with low readmission rates (0.6% within 48 hours, 1.4% over 3 months).

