patient had an emergency department visit on POD 20, due to an unrelated mechanical fall. Importantly, there were no major complications in either group requiring procedural interventions, new prescriptions, or additional interventions. Recently, a study by Kisby et al was published examining SDD after robotic-assisted sacrocolpopexy. In this retrospective study, 80 women underwent SDD compared to 192 who were discharged on  $\geq$ POD 1. This study found no difference in unplanned provider visits, emergency department visits or readmissions between the groups.

**We hypothesize that an ERAS protocol utilizing SDD for minimally invasive sacrocolpopexy is as safe as those that utilize discharge on POD 1 while incurring less total procedure-related costs and being acceptable as a post-op management plan for patients.** The *objective of this study* is to provide data which are necessary to widely implement SDD after a minimally invasive sacrocolpopexy. The results of this research *will have a significant impact* on increasing patient satisfaction, minimizing resource utilization, and improving clinical practice patterns in the field of urogynecology, both for this procedure and potentially other surgeries within our subspecialty.

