### **Research Plan**

#### **1. Study Design**

This is a prospective cohort study evaluating safety, cost and patient satisfaction with SDD for patients undergoing minimally invasive sacrocolpopexy for pelvic organ prolapse. A prospectively collected, historical control group who underwent the same surgical procedure will be utilized to compare these outcomes when applicable. SDD will be facilitated in part by a utilizing novel patient education video created for this study and implementing an ERAS pathway. All patients meeting eligibility criteria will be approached for study participation. Outcomes will be assessed on POD 0/1 and at the routine post-operative follow up visit, generally at 6 weeks after surgery.

**Primary outcomes:** The primary outcome of this study is serious adverse events.

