#### Post-operative Follow-up

- POD 0: All patients will be contacted by an individual on their surgical team to see how the patient is doing. If patients have a late discharge from the hospital, after 1700, a POD0 call will not be initiated. This call will last approximately 5 minutes in length (or as dictated by patient questions or concerns), to occur between 1500 and 1900 on day of surgery.
- POD 1: All patients will be contacted within 24 hours of their surgical completion time by a registered nurse or a physician. This call will last approximately 10 minutes in length.
- All patients will have a scheduled post-operative visit at ~6 weeks, as per our standard protocol.

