## **6. Research Environment**

SDD and ERAS protocols are part of a new initiative within the Women's Health Institute directed by our chair, [name]. The co-investigator and senior mentor on this project, [name], is the division director and is also committed to the success of this project. Lastly, this project has been discussed at multiple research

meetings and has the support of the other surgeons in the division, some of whom have successfully discharged patients same day after this surgery.

Regarding surgical volume, a chart review determined that ~60 minimally invasive sacrocolpopexies without concomitant rectopexy were performed within our division in 2016. Our Female Urology collaborator, who will be participating in this study, performs ~20 minimally invasive sacrocolpopexies per year. In 2017, we also had two new staff join the urogynecology division, who also perform this surgery and will be participating in subject recruitment. As such, we feel that our target recruitment is an achievable goal. Lastly, there are no current or planned clinical trials that could compete for subject recruitment for this study. Together, we feel that this environment is conducive to the implementation and successful execution of this research study.

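### Discharge day is named as the primary difference from the 60 historical controls, but the SDD cohort also receives a new video, an ERAS pathway and calls, and the controls' care is undescribed

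*Combined protocol and SAP*

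**What the plan says.** Section 4 (Statistical Plan) takes its comparison group for Aims 1 and 2 from a randomized mesh trial that finished recruiting in 2017. The 60 women are said to meet the present eligibility criteria and to share surgical approach, institutions and surgeons with the new cohort. The plan then states: "The primary difference is that participants in that study and the cohort proposed here is that all participants were discharged home on POD 1". It uses these women to compare adverse events and costs between SDD and POD 1 discharge. Logistic regression is to control for confounding, with no covariates named.

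Other sections describe what the SDD cohort receives:

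- **Video and ERAS.** Section 1 (Study Design): "SDD will be facilitated in part by a utilizing novel patient education video created for this study and implementing an ERAS pathway". The content of each is set out under Preoperative Visit and Day of Surgery.
- **Novelty of ERAS at the site.** Section 6 (Research Environment): "SDD and ERAS protocols are part of a new initiative within the Women's Health Institute directed by our chair". The Background says the same. Neither gives a start date.
- **Calls.** Post-operative Follow-up, POD 0: "All patients will be contacted by an individual on their surgical team to see how the patient is doing" (not made after a late discharge). POD 1: "All patients will be contacted within 24 hours of their surgical completion time by a registered nurse or a physician".

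On what ERAS pathways do, the Background says "they have been shown to shorten recovery, decrease hospital stay, reduce complications/nosocomial infections, and conserve resources". It states the hypothesis as "an ERAS protocol utilizing SDD for minimally invasive sacrocolpopexy is as safe as those that utilize discharge on POD 1".

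**The concern.** The comparison is labelled SDD versus POD 1, but the two groups differ, or may differ, in several other ways at once. By the protocol's own account, one of those elements improves both outcomes being compared: complications (Aim 1) and resource use (Aim 2).

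Aim 1 hypothesises no difference in adverse events. If ERAS lowers events and going home early raises them, the two effects can offset each other, and the result would read as evidence that early discharge is safe. Aim 2 hypothesises lower cost. Any saving produced by ERAS would be credited to discharge day, and the plan names no other comparator for cost.

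The hypothesis is most naturally read as ERAS with SDD against ERAS with POD 1 discharge. The controls are not shown to be an ERAS group.

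**Working it through.** **Step 1. What is known about each element in each group.**

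| Element | SDD cohort | 60 controls |
|---|---|---|
| Discharge | Same day intended | POD 1 |
| Education video | Yes | Absent: it was made for this study |
| ERAS pathway | Yes | Not stated |
| POD 0 and POD 1 calls | Yes | Not stated |
| Eligibility, approach, sites, surgeons | As planned | Stated to match |

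Only the video is certainly absent from the controls. That they lacked ERAS is an inference from ERAS being described as new and as being implemented here. That they lacked the calls is an inference from the calls being set out only for this study's patients.

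**Step 2. Can the planned analysis separate the elements?** Every SDD-cohort patient is offered the package, and no control had the video. If the controls also lacked ERAS and the calls, package and discharge day are the same variable, namely cohort. A regression on patient characteristics cannot divide one cohort coefficient into a package part and a discharge part.

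**Step 3. The plan's own figure.** This point has no figure of its own. The nearest is the 45.1% threshold. With n = 45, a reference of 26.3% and a one-sided exact binomial test at 0.05, the critical count is 18 (exact alpha 0.031). Power at 45.1% is 79.8%, so the figure reproduces. That calculation does not use the 60 controls.

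**Step 4. How much harm could be hidden.** Assume that the controls had no ERAS and that the effects multiply:

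observed ratio (SDD cohort / controls) = RR(ERAS) × RR(early discharge)

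The observed ratio equals 1 when RR(early discharge) = 1 / RR(ERAS). The documents give no value for RR(ERAS), so the values below are assumptions and include no effect. The last column applies RR(ERAS) to the 12% rate that the sample-size section considers more representative.

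| Assumed RR(ERAS) | Harm ratio that would show as no difference | Rate under ERAS with POD 1 discharge |
|---|---|---|
| 0.7 | 1/0.7 = 1.43 | 0.12 × 0.7 = 8.4% |
| 0.8 | 1/0.8 = 1.25 | 0.12 × 0.8 = 9.6% |
| 0.9 | 1/0.9 = 1.11 | 0.12 × 0.9 = 10.8% |
| 1.0 | 1/1.0 = 1.00 | 0.12 × 1.0 = 12.0% |

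**Step 5. What this does to the comparison of 45 with 60** (two-sided 0.05, normal approximation).

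- A true doubling, 24% versus 12%: power 37%.
- The same doubling with a package ratio of 0.7, 0.24 × 0.7 = 16.8% versus 12%: power 11%.
- A harm ratio of 1.43 with no package effect, 0.12 × 1.43 = 17.2% versus 12%: power about 11% to 12%, depending on the variance formula.

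The comparison is weak even without confounding. Confounding lowers the power further and, more importantly, changes what the estimate means.

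**The case against.** **The plan says primary difference, not only difference, and partly frames the question as a package.** The Background hypothesis concerns an ERAS protocol that uses SDD, Aim 1 speaks of an SDD protocol, and Study Design is open about the video and ERAS. This stands in part. But the Statistical Plan lists no other difference, and the Aim 1 and 2 hypotheses are worded as SDD against POD 1.

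**The controls may have had some of this care.** Fasting follows existing anesthesia protocols and the voiding trial is the division's standard one. ERAS has no stated start date. This stands. A reader might infer that the controls had no ERAS care; the documents do not say so. What they support is that the controls are not shown to have had it.

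**Masking needs ERAS to reduce the events that count.** The Background sentence is general. The same section also reports a prospective ERAS cohort in vaginal reconstructive surgery that showed no 30-day differences from historical controls. No passage says that ERAS lowers Clavien-Dindo grade 3 or higher events. This stands, and it is why a ratio of 1.0 belongs in the range.

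**The bias could run the other way.** The POD 1 call, the question about outside care at the 6-week visit, and the video's teaching on warning signs may bring more events to light in the SDD cohort. This stands. A reader might infer that the bias necessarily favours the hoped-for result; the direction is not established.

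**The primary rule does not use these controls.** Section 3 (Data Collection) compares the SDD proportion with a fixed 26.3% and calls a result below 45.1% non-inferior. This stands, so the point must not be read as invalidating that rule through the 60 controls. The documents do not describe the perioperative care behind the 26.3% either, so that comparison does not isolate discharge day.

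**Conclusion.** The concern holds as a limit on attribution. The stated primary difference omits one co-intervention that is certain (the video) and others that are possible (ERAS and the calls). The planned regression cannot separate from discharge day whatever coincides with cohort. As designed, the 60-control comparison can speak to the package against earlier care with POD 1 discharge. It cannot show that discharge day alone is as safe or cheaper, unless the controls' care proves comparable.

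The size is unknown. Under the assumptions of multiplicative effects, controls without ERAS, and an ERAS risk ratio of 0.7 to 1.0, the hidden harm ratio is 1.43 to 1.00. The stronger reading, that harm will be masked, is not supported: no ERAS effect size is given, a related cohort found no 30-day difference, and event capture may be fuller in the SDD group. The point applies to the event and cost comparisons for Aims 1 and 2, and matters most for cost, which has no other comparator.

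**What to change.** 1. In section 4, replace the statement of a single primary difference with a list: discharge day and the video as known differences; the ERAS pathway and the POD 0 and POD 1 calls as possible ones.
2. Extract from the EMR which ERAS elements and which calls each of the 60 controls received, and tabulate these by cohort.
3. Word the Aim 1 and Aim 2 conclusions as the package (ERAS, video, calls and SDD) versus earlier care with POD 1 discharge. State in advance that no claim about discharge day alone will be made unless the tabulation shows that the controls' care was comparable.
4. Note in the same place that event capture may differ between the cohorts, and in which direction that could act.

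The cost is a modest chart extraction for 60 women and a narrower conclusion. No added patients, change in care or change in sample size is needed.
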